5.2 Secondary Efficacy Endpoints

The Study Subjects shall show no adverse conditions during the study. If adverse conditions are realized during the study, the root cause analysis shall be performed and a determination shall be made as to the safety of the study product.

5.3 Safety Evaluations

Incidence of adverse events shall be addressed immediately and appropriate action shall be taken to ensure the safety of the Study Subjects. Any adverse event occurrences shall be analyzed and documented.

6 SUBJECT SELECTION

6.1 Study Population

Subjects with a potential diagnosis of peptic ulcer disease who meet the inclusion and exclusion criteria will be eligible for participation in this study.

6.2 Inclusion Criteria

- Male or female ≥ 18 years of age at the time of the visit.
- Patients who are experiencing the effects of gastritis.
- Written informed consent (and assent when applicable) obtained from subject and ability for subject to comply with the requirements of the study.

6.3 Exclusion Criteria

- Pregnant or lactating women.
- Study Subjects currently taking antibiotics
- Presence of a condition or abnormality that in the opinion of the Investigator would compromise the safety of the patient or the quality of the data.
- Fasting required one hour prior to testing.
- Study Subjects shall not consume the following items prior to the test.
 - Mouthwash
 - Chewing gum
 - Carbonated beverages
 - Cigarette smoke
 - Acetone (to simulate the effect of ketone production that may result from some diets)
 - Alcohol

7 CONCURRENT MEDICATIONS

All subjects should be maintained on the same medications through the individual's entire study period, as medically feasible, with no introduction of new chronic therapies.

7.1 Allowed Medications and Treatments

Standard therapy for gastritis is allowed except for treatments noted in the exclusion criteria described above and as noted in the prohibited medications section below.

Prohibited Medications and Treatments

- The patient should have fasted at least one hour before administering the ARJ C13 Breath Test System.

8 STUDY TREATMENTS

8.1 Method of Assigning Subjects to Treatment Groups

Approximately 100 - 300 eligible patients will be assigned to the ARJ C13 Breath Test System.

8.2 Formulation of Test and Control Products

The study is to be performed the same across the entire population of each study group. Each Study Subject shall be tested with the study product which is ARJ C13 Breath Test Kit. Each Study Subject shall be observed by the Investigator or designee during the testing. This is common for all Study Subjects.

8.2.1 Formulation of Test Product

ARJ Medical's C13 Urea Test Kit consists of one sealed packet of premeasured C13 urea, one packet of premeasured citric acid and sweetener and two breath bags to be used for the exhaled breath to be measured. At the time of testing, the sealed packet of premeasured C13 urea shall be opened and the citric acid and sweetener shall be added to the packet. The packet will then be filled with water and the Study Subject shall drink the contents of the packet until empty. See Table 1 for the formulation of ARJ C13 Urea Test.

Table 1: Formulation and Measurement

| | ARJ C13 Urea Breath Test |
|------------------------------|--------------------------|
| 13C Urea | 75 mg |
| Citric Acid Flavoring Packet | Range of 2-4 g |
| | |

8.2.2 Formulation of Control Product

The ARJ Pylo Plus test is performed by evaluating a sample of the study subject's biopsy.

8.2.3 Packaging and Labeling

Study drug is supplied in single use kits.

Each carton (kit) of study drug will be labeled with the required FDA warning statement, the protocol number, a treatment number, the name of the Sponsors, and directions for patient use and storage. Each test kit will be labeled with Protocol ID and Protocol Title and the statement "For investigational use only":

8.3 Supply of Study Drug at the Site

The Study Sponsor (or designee) will deliver study product to the investigational site. The initial study product delivery will be delivered after site activation (i.e., all required regulatory documentation has been received by the Sponsor and a contract has been executed). Subsequent study product deliveries will be made after site request for resupply.

8.3.1 Dosage/Dosage Regimen

The test subjects shall mix the urea and citric acid together in the provided packet and fill the cpacket with water. After mixing the contents of the packets the Study Subject shall ingest the packets liquid until the packet is empty.

8.3.2 Dispensing

The test subjects shall be provided with the study product or the comparator product by the Investigator or designee who shall administer the testing.

8.3.3 Administration Instructions

Upon the Study Subject's initial arrival at the study site, the study Investigator shall provide the study subject with their study record which includes their Study Subject identification and log into the study by entering:

- Study Subject ID (Name or Number)
- Date

The study Investigator or designee shall record the Study Subject's arrival by documenting it on the Study Subjects' Study Activity Form which will include:

- Study Subject's ID
- Date of Test
- Review of current health and health statistics
- Study Product ID Distributed to the Study Subject
- Consumption Time of Study Product
- Exhale Time and Analyzer Reading
- Review of current health and health statistics
- Adverse Events documentation

8.4 Supply of Study Drug at the Site

The study Sponsor shall supply the study product and comparator test product to the test site to ensure sufficient quantities to maintain the testing without interruption. The Sponsor and Investigator shall agree on the minimum quantity of study product to be available on the premises of the study site to ensure availability of the study product for the Study Subjects through the term of the study.

8.4.1 Storage

ARJ C13 Urea Test System shall be stored at room temperature which would be approximately 25°C (77°F); excursions permitted to 15-30°C (59-86°F). The following components of the test kits have expiration dates: the 13C-urea powder and the Citric Acid Powder. Do not use either of these components beyond the expiration date stated on the respective labels.

The comparator product, ARJ Pylo Plus storage is at room temperature for up to two (2) years. Do not use beyond the expiration date.

8.5 Measures of Treatment Compliance

Subjects will be asked to log into the Study Subject Test Log by entering their respective Study Subject Identification and date.

9 STUDY PROCEDURES AND GUIDELINES

A Schedule of Events representing the required testing procedures to be performed for the duration of the study is diagrammed in Appendix 1.

Prior to conducting any study-related activities, written informed consent and the Health Insurance Portability and Accountability Act (HIPAA) authorization must be signed and dated by the subject. If appropriate, assent must also be obtained prior to conducting any study-related activities.

9.1 Clinical Assessments

9.1.1 Concomitant Medications

All concomitant medication and concurrent therapies will be documented at Baseline/Screening and at day of testing. Dose, route, unit frequency of administration, and indication for administration and dates of medication will be captured.

9.1.2 Demographics

Demographic information (date of birth, gender, race) will be recorded at Screening.

9.1.3 Medical History

Relevant medical history, including history of current disease, other pertinent respiratory history, and information regarding underlying diseases will be recorded at Screening.

9.1.4 Physical Examination

A complete physical examination will be performed by either the investigator or a sub-investigator who is a physician at the subject's Screening. Qualified staff (MD, NP, RN, and PA) may complete the abbreviated physical exam at day of Subject's testing. New abnormal physical exam findings must be documented and will be reviewed with the physician prior to continuing with the Subjects test.

9.1.5 Vital Signs

Upon arrival for the second testing, the body temperature, blood pressure, pulse and respirations will be performed per physician typical protocol.

9.1.6 Adverse Events

Incidence of Adverse Events shall be identified and documented by the Study Subject and also by the Investigator during the testing and observation review. Any and all Adverse Events shall be documented in the Study Subjects' testing log and also recorded and tracked by the Investigator to be analyzed within the study statistics. If the Study Subject and/or the Investigator determine the Adverse Event was presented by the use of the C13 Urea Test kit the use of the study product shall be immediately terminated and necessary actions shall be taken to improve the Study Subject's condition.

9.2 Clinical Laboratory Measurements

None

10 EVALUATIONS BY VISIT

10.1 Visit 1 Screening and Test (Day 1)

1. Review the study with the subject and obtain written informed consent and HIPAA authorization and assent, if appropriate.
2. Assign the subject a unique screening number.
3. Record demographics data.
4. Record medical history, including a history of gastritis, diagnosis date, and prior gastritis treatments.
5. Record concomitant medications.
6. Perform and record vital signs.
7. Schedule subject for Visit 2 to perform study test (may be same day).
8. List all additional procedures, Dispense study drug (if same day)

10.2 Visit 2 - Study Test

1. Concomitant medications review (if not same day).
2. Perform and record vital signs.

10.3 Early Withdrawal Visit

1. Record any Adverse Experiences and/or for adverse experiences and exclusionary medication use.

2. Record changes to concomitant medications.
3. Perform and record vital signs.

11 ADVERSE EXPERIENCE REPORTING AND DOCUMENTATION

11.1 Adverse Events

An adverse event (AE) is any untoward medical occurrence in a clinical investigation of a patient administered a pharmaceutical product and that does not necessarily have a causal relationship with the treatment. An AE is therefore any unfavorable and unintended sign (including an abnormal laboratory finding), symptom or disease temporally associated with the administration of an investigational product, whether or not related to that investigational product. An unexpected AE is one of a type not identified in nature, severity, or frequency in the current Investigator's Brochure or of greater severity or frequency than expected based on the information in the Investigator's Brochure.

The Investigator will probe, via discussion with the subject, for the occurrence of AEs during each subject visit and record the information in the site's source documents. Adverse events will be recorded in the patient CRF. Adverse events will be described by duration (start and stop dates and times), severity, outcome, treatment and relation to study drug, or if unrelated, the cause.

AE Severity

The National Cancer Institute's Common Terminology Criteria for Adverse Events (CTCAE) Version 3.0 should be used to assess and grade AE severity, including laboratory abnormalities judged to be clinically significant. The modified criteria can be found in the study manual. It should be pointed out that the term "severe" is a measure of intensity and that a severe AE is not necessarily serious.

AE Relationship to Study Drug

The relationship of an AE to the study drug should be assessed using the following the guidelines in Table 12.

Table 1. AE Relationship to Study Drug

| Relationship to Drug | Comment |
|----------------------|---------------------------------------------------------------------------------------------------------------------------------------------------------------------------------------------------------------------------------------------------------------------------------------------------------------------------------------------------------------|
| Definitely | Previously known toxicity of agent; or an event that follows a reasonable temporal sequence from administration of the drug; that follows a known or expected response pattern to the suspected drug; that is confirmed by stopping or reducing the dosage of the drug; and that is not explained by any other reasonable hypothesis. |
| Probably | An event that follows a reasonable temporal sequence from administration of the drug; that follows a known or expected response pattern to the suspected drug; that is confirmed by stopping or reducing the dosage of the drug; and that is unlikely to be explained by the known characteristics of the subject's clinical state or by other interventions. |
| Possibly | An event that follows a reasonable temporal sequence from administration of the drug; that follows a known or expected response pattern to that suspected drug; but that could readily have been produced by a number of other factors. |
| Unrelated | An event that can be determined with certainty to have no relationship to the study drug. |

11.2 Serious Adverse Experiences (SAE)

An SAE is defined as any AE occurring at any dose that results in any of the following outcomes:

- death
- a life-threatening adverse experience
- inpatient hospitalization or prolongation of existing hospitalization

- a persistent or significant disability/incapacity
- a congenital anomaly/birth defect

Other important medical events may also be considered an SAE when, based on appropriate medical judgment, they jeopardize the subject or require intervention to prevent one of the outcomes listed.

11.2.1 Serious Adverse Experience Reporting

The study site will document all SAEs that occur (whether or not related to study drug) per UCSF CHR Guidelines. The collection period for all SAEs will begin after informed consent is obtained and end after procedures for the final study visit have been completed.

In accordance with the standard operating procedures and policies of the local Institutional Review Board (IRB)/Independent Ethics Committee (IEC), the site investigator will report SAEs to the IRB/IEC.

12 DISCONTINUATION AND REPLACEMENT OF SUBJECTS

12.1 Early Discontinuation of Study

A subject may be discontinued from study treatment at any time if the subject, the investigator, or the Sponsor feels that it is not in the subject's best interest to continue. The following is a list of possible reasons for study treatment discontinuation:

- Subject withdrawal of consent (or assent)
- Subject is not compliant with study procedures
- Adverse event that in the opinion of the investigator would be in the best interest of the subject to discontinue study treatment
- Protocol violation requiring discontinuation of study treatment
- Lost to follow-up
- Sponsor request for early termination of study
- Positive pregnancy test (females)

If a subject is withdrawn from treatment due to an adverse event, the subject will be followed and treated by the Investigator until the abnormal parameter or symptom has resolved or stabilized.

All subjects who discontinue study treatment should come in for an early discontinuation visit as soon as possible to ensure proper closure of the subject's participation in the study and to confirm the subject has no adverse conditions.

All subjects are free to withdraw from participation at any time, for any reason, specified or unspecified, and without prejudice.

Reasonable attempts will be made by the investigator to provide a reason for subject withdrawals. The reason for the subject's withdrawal from the study will be specified in the subject's source documents Refer to Section 10 for early termination procedures.

12.2 Replacement of Subjects

Subjects who withdraw from the study will be replaced.

13 PROTOCOL VIOLATIONS

A protocol violation occurs when the subject, investigator, or Sponsor fails to adhere to significant protocol requirements affecting the inclusion, exclusion, subject safety and primary endpoint criteria. Protocol violations for this study include, but are not limited to, the following:

Failure to meet inclusion/exclusion criteria

Use of a prohibited concomitant medication

Failure to comply with Good Clinical Practice (GCP) guidelines will also result in a protocol violation. The Sponsor will determine if a protocol violation will result in withdrawal of a subject.

When a protocol violation occurs, it will be discussed with the investigator and a Protocol Violation Form detailing the violation will be generated. This form will be signed by a Sponsor representative and the Investigator. A copy of the form will be filed in the site's regulatory binder and in the Sponsor's files.

14 STATISTICAL METHODS AND CONSIDERATIONS

Prior to the analysis of the final study data, a detailed Statistical Analysis Plan (SAP) will be written describing all analyses that will be performed. The SAP will contain any modifications to the analysis plan described below.

14.1 Data Sets Analyzed

All eligible patients who are randomized into the study and receive at least one dose of the study drug (the Safety Population) will be included in the safety analysis.

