| RATIONALE | 
Patients who are experiencing the effects of gastritis, which is an inflammation, irritation, or erosion of the lining of the stomach require an identification of the status and generation of urease in the stomach to provide a definitive diagnosis. Historically, this has been achieved via an upper endoscopy, where a thin tube containing a tiny camera, is inserted through your mouth and down into your stomach to look at the stomach lining. The doctor will check for inflammation and may perform a biopsy, a procedure in which a tiny sample of tissue is removed and then sent to a laboratory for analysis.
 
By ingesting a low dosage of C13 urea, the patients' exhaled breath is then measured to record the level of change of ^{13}C labeled urea detectable in a patient's breath. This is measured before and after the ingestion of the urea mixture. The exhaled breath is read by the analyzer which provides an immediate diagnoses and is non-invasive. Although other C13 Urea Test Kits and analyzers are in the market, the ARJ C13 Breath Test System is believed to be equivalent in functionality and will be manufactured in the U.S. which can provide a cost effective equivalent product.
 |
| STUDY DESIGN | Up to 3 centers, non-randomized, comparative study to compare the ARJ C13 Urea Breath Test System to the ARJ Pylo Plus rapid urease test. |
| PRIMARY OBJECTIVE | To demonstrate the ARJ C13 Breath Test System equivalency to the predicate ARJ Pylo Plus rapid urease test. |
| SECONDARY OBJECTIVES | None |
| NUMBER OF SUBJECTS | Test Group: Approximately 100 - 300 Study Subjects |
| SUBJECT SELECTION CRITERIA | 
Inclusion Criteria:
 
 • Male or Female \geq 18 years of age • Patients who are experiencing the effects of gastritis • Written informed consent (and assent when applicable) obtained from subject and ability for subject to comply with the requirements of the study. 
Exclusion Criteria:
 
 • Pregnant or lactating female • Study Subjects currently taking antibiotics • Presence of a condition or abnormality that in the opinion of the Investigator would compromise the safety of the patient or the quality of the data • Fasting required one hour prior to testing • Study Subjects shall not consume the following items prior to the test 
 ○ Mouthwash |

| | |

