| STATISTICS Primary Analysis Plan | Each review of the subject(s) shall be recorded including documentation of status at selection and again during the comparative study test visit. The baseline reading and each subsequent breath test shall provide a complete series of breath readings per Study Subject. The analyzed breath readings shall be documented. The analysis of the results shall be graphed for the Study Group. This is to illustrate progression from start of the testing through the most recent day's tests of the study. At the end of the study, the results of the Study Group's ARJ C13 Breath Test System shall be compared to the results of the ARJ Pylo Plus, histology, rapid urease and culture results as compared per study subject. The Study Group's results shall be calculated and compared for equivalency. Adverse Events shall be documented by subject. All identified Adverse Events shall be given a level of adversity per Table 3- AE Severity Grading. The analysis of the results shall be graphed per subject and overall of all subjects per study group. This is to illustrate adversity from start of testing through the most recent testing per study group. |
| Rationale for Number of Subjects | The clinical studies for the ARJ C13 Urea Breath Test predicate device Pylo-Plus (K052708) included 100 study subjects. The recent clearance (May 2013) of the Exalenz Bioscience Ltd. Breath ID Hp System (K130524) included 79 pre-treatment study subjects. The rationale to use approximately 100 - 300 study subjects shows equivalency to the two (2) related clinical studies. |

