4 STUDY DESIGN

4.1 Study Overview

This will be up to three sites, open label, comparative trial. Approximately 100 – 300 (number) of subjects are planned. Each subject will be administered a single dose of study drug one time during a single visit. Evaluations will be taken at baseline and at a specified time during the testing session.

Screening data will be reviewed to determine subject eligibility. Upon patient's consent, subjects who meet all inclusion criteria and none of the exclusion criteria will be entered into the study.

The following testing regimens will be used:

- Using three independent sites, a total of 100-300 clinical samples are to be obtained from a population of symptomatic individuals who have been prescribed endoscopic examination for the detection of H.Pylori infection. The physician(s) will schedule test subjects per standard of care for an endoscopy procedure in which a gastric mucosal biopsy will be obtained. In addition to the physician's standard testing, the obtained tissue will also be used to perform the following tests:
 - Histology
 - Rapid Urease Test
 - Culture
- Experimental treatment ARJ C13 Urea Test dosage shall be a one-time dosage at time of initial testing.
- Comparator – ARJ Pylo Plus shall be a one-time test performed during a follow-up visit to examine the study subject's biopsy to determine the level of urease presence.
- Total duration of subject participation will be two visits. Total duration of the study is expected to be 4 months.

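### Section 14.1 defines the Safety Population by eligibility and randomization in a non-randomized study, so adverse events in dosed but ineligible subjects could be left out of the safety analysis

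*Combined protocol and SAP*

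**What the plan says.** Section 14.1 names one analysis set, and its members must meet three conditions together: "All eligible patients who are randomized into the study and receive at least one dose of the study drug (the Safety Population").

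On allocation, the Synopsis (Study Design) describes a "non-randomized, comparative study to compare the ARJ C13 Urea Breath Test System", and section 8.1 has a single assignment: "eligible patients will be assigned to the ARJ C13 Breath Test System".

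On the scope of the adverse-event analysis, three other places set no eligibility or randomization condition:
- Synopsis, Primary Analysis Plan: all identified events are graded, and the results are "graphed per subject and overall of all subjects per study group".
- Section 5.3: "Any adverse event occurrences shall be analyzed and documented".
- Section 9.1.6: events are to be "recorded and tracked by the Investigator to be analyzed within the study statistics".

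Section 14 promises a separate SAP before the final data are analysed. The Synopsis (Safety Evaluations) plans an interim safety analysis at about 20% of patients.

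**The concern.** A safety set should contain everyone exposed to the product. This one also requires randomization, which never happens in the study, and eligibility, without saying when eligibility is judged.

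Eligibility matters because people who took the product despite an exclusion are the ones whose events a reader would least want to lose. If section 14.1 is applied over the broader statements and eligibility is judged after the fact, their events could drop out of the final safety analysis. The same could happen at the interim if no SAP has replaced section 14.1 by then. If instead all events are counted but the section 14.1 set supplies the denominator, the event rate is overstated.

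**Working it through.** **1. The randomization condition.** Section 14.1 requires it; the Synopsis says the study is non-randomized; section 8.1 assigns every subject to the breath test. Taken literally, 0 of the planned 100–300 subjects belong to the Safety Population. The word is probably leftover text for enrolled or entered.

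**2. The eligibility condition, with *randomized* read as enrolled.**
- *Judged at entry.* Section 4.1 says "Screening data will be reviewed to determine subject eligibility", and only those who pass are entered. On this reading 0 dosed subjects are dropped.
- *Judged retrospectively.* Dosed subjects later found ineligible are dropped.

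No section chooses between these readings.

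**3. Whether dosed but ineligible subjects are foreseen.** They are:
- Section 13 lists failure to meet the entry criteria as a violation and adds: "The Sponsor will determine if a protocol violation will result in withdrawal of a subject". Section 12.2 replaces subjects who withdraw.
- Section 6.3 places fasting and items not to be consumed before the test among the exclusion criteria. A lapse may come to light only after dosing.
- Pregnancy is an exclusion (6.3), and a positive test is a possible reason for discontinuation (12.1). No pregnancy test is listed in sections 9.2 or 10.1 or in Appendix 1.
- Section 10.3 has the early withdrawal visit record use of exclusionary medication.

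**4. Illustrative size under the retrospective reading.** The documents give no ineligibility rate. I assume r = 2% to 10% of dosed subjects; under the entry reading r has no effect.

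Subjects dropped = n × r:

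| n | r = 2% | r = 10% |
|---|---|---|
| 100 | 2 | 10 |
| 300 | 6 | 30 |
| 20 (20% interim of 100) | 0.4 | 2 |
| 60 (20% interim of 300) | 1.2 | 6 |

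One-sided 95% upper bound when no event is seen = 1 − 0.05^(1/n):

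| Planned n | All dosed | After 2% dropped | After 10% dropped |
|---|---|---|---|
| 100 | 2.95% (n = 100) | 3.01% (n = 98) | 3.27% (n = 90) |
| 300 | 0.99% (n = 300) | 1.01% (n = 294) | 1.10% (n = 270) |

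Relative overstatement if all events are divided by the reduced set = 1/(1 − r) − 1:
- r = 2%: 1/0.98 − 1 = 2.0%
- r = 5%: 1/0.95 − 1 = 5.3%
- r = 10%: 1/0.90 − 1 = 11.1%

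**5. Related inconsistencies.** Appendix 1 titles Visit 1 as the breath-test visit but marks study-drug administration and adverse experiences only at Visit 2. Section 4.1 puts the dose at initial testing, section 10.1 allows it on the screening day, and section 10.2 titles Visit 2 as the study test. Section 11.1 asks about adverse events at every visit. A minor point: in the section 11.1 relationship table, *Probably*, and *Definitely* unless the toxicity is already known, depend on stopping or reducing the dose. That does not fit the single dose in section 4.1.

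**The case against.** The strongest reply is that this is a wording slip with a harmless natural reading. No analyst would run a safety analysis on nobody. Sections 4.1 and 8.1 both use eligibility as an entry status, and on that reading no dosed subject is lost. No section says a withdrawn subject's data are discarded, and sections 10.3 and 12.1 have events in such subjects recorded and followed. Harm needs several things together: retrospective eligibility, section 14.1 prevailing over the broader statements, no correction in the SAP, and an event in a subject dosed in error. The 2–10% rate is an assumption.

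Much of this is right as a limit on consequence. The literal count of zero shows a contradiction, not a likely outcome. Collection is not at risk, since sections 8.3.3, 9.1.6 and 11.1 already require recording; only inclusion in the analysis is. Appendix 1 is headed as an example, although section 9 relies on it, and a Visit 2 check can still pick up events after a Visit 1 dose. That mismatch is therefore only a risk of missed entries. No described analysis uses the relationship grade.

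The reply does not remove the defect. The harmless reading is available, but nothing in the plan selects it. The promised SAP is required only before the final analysis, so it need not exist at the 20% safety look. If the broader statements are meant to govern, section 14.1 is wrong as written.

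One further point stands in part: section 11.2.1 collects serious events from consent, so a set defined by ingestion leaves out consented subjects who were never dosed.

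**Conclusion.** The concern holds. Section 14.1 contradicts the non-randomized design and is narrower than the Synopsis analysis plan and sections 5.3 and 9.1.6. That conclusion rests on the text alone and needs no assumed figure.

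The consequence is conditional. It ranges from no dosed subject lost (eligibility at entry) to an unknown number (eligibility judged later). Even at the top of the assumed range the loss of precision is small. What matters is the possible omission of events in exposed subjects who had an exclusion, or a modestly inflated rate if numerator and denominator come from different sets. The primary comparison of the breath test with the comparator is untouched. This should be corrected, but it does not threaten the trial's main result.

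**What to change.** Redefine the Safety Population in section 14.1 as all subjects who ingest any of the 13C-urea solution, regardless of eligibility, withdrawal or replacement. Delete the randomization condition. State that this set supplies both events and denominator for the interim and final safety analyses, in line with the Synopsis and sections 5.3 and 9.1.6. Serious events in consented but undosed subjects can be listed separately.

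Mark adverse experiences at both visits in Appendix 1, to match section 11.1. Sections 4.1, 10.1 and 10.2 and Appendix 1 must be reconciled on the visit at which the study drug is given. As a minor matter, the relationship table in section 11.1 must be reconciled with the single administration in section 4.1.

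The cost is a few wording changes plus that reconciliation. No new procedure or data item is needed, because adverse-event recording is already required.
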